12.3.4 Rationale for Selected Analysis Method for the Primary Endpoint

The MMDs are considered continuous data, and they are analysed using methods based on observations following a normal distribution. Given the repeated observation of normally distributed data, an MMRM analysis using all available data has been chosen for the primary analysis. Covariates are included in the model based on an approach including key factors representing study design features (month, treatment, MHD stratum, country), and baseline MMD score to account for differences in baseline MMDs and its predictive ability. When the MMRM analysis includes the individual factors mentioned as well as interaction of month and treatment, month and baseline score, and month and stratum, and applies an unstructured covariance, as described in Section 12.3.1, it allows for flexibility in modelling the development over time and similarly provides robust estimation, even under some deviation from the assumption of normality.

The use of MMRM combined with the rules for handling missing data in this set-up allows for inclusion of the majority of the patients, even if they only have limited data observed.

12.3.5 Sensitivity Analyses of the Primary Endpoint

Imputations for Withdrawals Due to Adverse Event or Lack of Efficacy

To explore the assumptions related to how patients withdrawing due to adverse events or lack of efficacy are behaving, an analysis similar to the primary analysis will be conducted, where monthly values for all patients are calculated using the *prorating* imputation rule described in Section 19.1.1.1 without penalization for early withdrawal due to adverse events or lack of efficacy as was done for the primary estimand. This means that the number of MMDs for all patients will be calculated according to rows 1-3 in Panel 5, even if patients are withdrawing due to lack of efficacy or adverse events.

Imputation for Weeks 1-4

To explore the robustness of the results to missing eDiary data in the first 4 weeks after infusion, an analysis similar to the primary analysis will be conducted, where monthly values in the first 4 weeks after first infusion are calculated using the *weighting* rule described in Section 19.1.1.1 if patients have less than 14 days with eDiary reporting in this period. This means that baseline values will be used in the calculation of Weeks 1-4 values for patients with less than 14 days of eDiary data in the 4 weeks after first infusion.

12.3.6 Supplementary Analyses of the Primary Endpoint

To provide additional insight into the understanding of the treatment effect, a supplementary analysis for the primary estimand will be conducted.

The supplementary analysis will be a repetition of the primary analysis for the change from baseline in number of MMDs but without differentiating between headaches where patients took medication to treat their headache and headaches where patients took medication to treat their headache because they believed they were having a migraine. This means that a day will be counted as a migraine day by changing criterion D in Section 4.5.1 to:

• Patient took medication to treat the headache.

12.3.7 Covariate Investigation and Subgroup Analyses of the Primary Endpoint

Subgroup analyses will be performed, where relevant, using the model specified in Section 12.3.2 on the set of patients included in the subgroup. For EM/CM and low/high frequency EM and CM (see below), the terms with stratum will be excluded from the model.

The subgroups that will be investigated are

- Sex
- Race: White and other
- EM (MMDs ≥ 4, MHDs ≤ 14) and CM (MMDs ≥ 8, MHDs >14) (based on baseline MMDs and MHDs derived according to the definitions in Section 4.5 and the descriptions in Section 19.1.1.1)
- Age group: \leq 35 years and >35 years

- Medication overuse headache diagnosis
- Number of failed previous treatments (2 and > 2)
- Low frequency EM (4 ≤ MMDs < 8), high frequency EM (8 ≤ MMDs ≤ 14), and CM (MMDs ≥ 8) based on baseline MMDs and MHDs derived according to the definitions in Section 4.5 and the descriptions in Section 19.1.1.1.

The assumption of equal treatment effect across subgroups will be investigated on an exploratory basis for all subgroups listed above by adding the three-way interaction term subgroup-by-treatment-by-week to the model. A test for whether the 3-way interaction term and the 2-way interaction (subgroup-by-treatment) term can be removed from the model will be performed by comparing the model without both the 3-way interaction term and the subgroup-by-treatment 2-way interaction term to the model with the 3-way interaction term. This will be done by fitting both models using (maximum likelihood) ML and making a likelihood ratio test comparing -2*log(Q) to the asymptotic X^2 distribution, where Q is the quotient of the maximised likelihood functions. The p-value for this test will be reported.

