12.3.2 Primary Analysis of the Primary Endpoint

Changes from Baseline in MMDs at the 6 first 4-week intervals will be analysed using a restricted maximum likelihood (REML)-based mixed model for repeated measures (MMRM) approach. The analysis will be performed using all available monthly scores for the first 6 months in the study derived as specified in Section 19.1.1. Below, the term "month" refers to 4-week periods.

The model will include the following fixed effects: month (Weeks 1-4, Weeks 5-8, Weeks 9-12, Weeks 13-16, Weeks 17-20, and Weeks 21-24), country, stratification factor (MHDs at baseline: $\leq 14/>14$) and treatment as factors, baseline MMDs as a continuous covariate, treatment-by-month interaction, baseline score-by-month interaction, and stratum-by-month interaction. An unstructured variance structure will be used to model the within-patient errors. If, unexpectedly, this analysis fails to converge, the following variance structures will be tried out, in the following order: first-order ante-dependence, heterogenous compound symmetry, compound symmetry, and the first to converge will be applied. The Kenward-Roger approximation will be used to estimate denominator degrees of freedom. The SAS[®] code for the primary analysis is shown in Appendix IV.

The mean differences between each dose of eptinezumab and placebo will be estimated based on the least squares means for the treatment-by-month interaction in the MMRM model. The estimates will be presented with p-values and 95% CIs. The primary comparisons will be the contrasts between each dose of eptinezumab and placebo averaged across Weeks 1-12. These averaged contrasts are obtained by weighting together the first 3 monthly least squares mean estimates for each dose. More specifically, they are computed via the matrix product: $kL\hat{\beta}$, where L is the $18 \times p$ coefficient matrix used for computing the least squares mean estimates for the treatment-by-month interaction effects, $\hat{\beta}$ is the $p \times 1$ vector of parameter estimates, and k is a 1×18 vector of coefficients, which for the comparison between eptinezumab 100 mg and placebo is defined as:

$$k = \left(\frac{1}{3}, \frac{1}{3}, \frac{1}{3}, 0_9, -\frac{1}{3}, -\frac{1}{3}, -\frac{1}{3}, 0_3\right),$$

and for the comparison between eptinezumab 300 mg and placebo is defined as:

$$k = \left(0_6, \frac{1}{3}, \frac{1}{3}, \frac{1}{3}, 0_3, -\frac{1}{3}, -\frac{1}{3}, -\frac{1}{3}, 0_3 \right),$$

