For patients with any post-baseline suicidal ideation or behaviour in the Placebo-controlled Period (C-SSRS scores of 1 to 10), listings will be provided based on APRS including all C-SSRS scores prior to entering the Extension Period for those patients for inclusion in the *CSR*.

A similar listing will be provided for patients with any post-baseline suicidal ideation or behaviour in the Extension Period including all the C-SSRS scores for those patients for inclusion in the *addendum to CSR*.

14 Blinded Data Reviews

The quality of the study will be overseen by performing blinded data reviews during the conduct of the study. The reviews may include, but are not limited to, data quality, protocol adherence, and the appropriateness of design assumptions, including the sample size assumptions.

An independent Safety Data Monitoring Committee (DMC) will regularly monitor the patients' safety data according to the *DMC Charter*. The DMC will have access to unblinded information for the double-blind treatment for each patient. Members of the DMC will not be involved in other study-related tasks.

15 Interim Analyses

See Section 18.

16 Sample Size Considerations

The two prior eptinezumab Phase III studies, PROMISE-1 performed in an EM population and PROMISE-2 performed in a CM population, had the following effect sizes for the primary endpoint when compared to placebo (standard deviations):

- EM: 100 mg 0.69 (3.1), 300 mg 1.11 (3.1)
- CM: 100 mg 2.03 (5.8), 300 mg 2.60 (5.8)

The power was determined by simulating the testing strategy (10000 simulations) assuming normal distributions with similar mean and SD for continuous endpoints and similar success rates as the response variables in the Phase III studies for the corresponding population (EM or CM) without assuming the variables to be correlated. With 280 patients per treatment group, assuming that 40% of the patients will be from the EM population and 60% from the

CM population, and that 2% of the patients not having a post-baseline assessment of the primary endpoint, simulations show that the power for the test of the primary endpoint is approximately 94% for the comparison of 100 mg to placebo and 99% power for the comparison of 300 mg to placebo. The individual key secondary endpoints had a power of at least 68% for showing an effect, with a combined power of 58% for seeing an effect for all primary and key secondary endpoints and both doses in the testing strategy.

17 Statistical Software

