Appendix IV SAS[®] Code

SAS[®] Code

Primary Analysis

The SAS[®] code for the primary analysis of the primary endpoint described in Section 12.3.2 is given below. Here, it is assumed that the ordering of the levels of the treatment factor is: 100 mg, 300 mg, placebo.

```
proc mixed data = xxxx method = REML;
class USUBJID TRTP(ref = 'Placebo') STRATUM COUNTRY AVISITN;
model CHG = BASE TRTP AVISITN STRATUM COUNTRY BASE*AVISITN
STRATUM*AVISITN TRTP*AVISITN / DDFM = KR;
repeated AVISITN / subject = USUBJID type = UN;
lsmestimate TRTP*AVISITN "100 mg vs. Placebo, Weeks 1-12"
[1, 1 1] [1, 1 2] [1, 1 3] [-1, 3 1] [-1, 3 2] [-1, 3 3]/
divisor = 3 cl;
lsmestimate TRTP*AVISITN "300 mg vs. Placebo, Weeks 1-12"
[1, 2 1] [1, 2 2] [1, 2 3] [-1, 3 1] [-1, 3 2] [-1, 3 3]/
divisor = 3 cl;
```

run;

Key Secondary Analysis

The SAS[®] code for conducting the key secondary analyses described in Section 12.4.2 is given below. Note that p-values to be included in the test strategy will be computed from a likelihood ratio test.

run;

Secondary Analysis

The SAS[®] code for computing p-values from the extended CMH test for the secondary endpoints described in Section 12.5 is given below. The p-values are computed separately for each active treatment group. In the code below the relevant p-value is stored in the p_value output data set.

```
proc freq data = xxxx (where = (TRTP in ('EPTI xxx mg' 'PBO') and AVISIT =
'xxxx'));
    output out = p_value CMHRMS;
```

```
tables STRATUM*TRTP*AVAL / cmh2;
run;
```

Sensitivity Analysis (placebo-based Multiple Imputation)

The SAS[®] code that will be the basis for the placebo-based multiple imputation (pMI) sensitivity analysis for the key secondary endpoint, HIT-6, mentioned in Section 12.4.4, is given below. Note that data transformation steps are omitted and only the most crucial parts are shown.

The procedure for the pMI method will include the following steps:

- 1. Impute missing intermittent data using Markov Chain Monte Carlo (MCMC) methodology by treatment group with the model for HIT-6 total score at baseline and at Week 4, 8, 12, 16, 20, and 24, using PROC MI from SAS[®], with seed = 101990 and 200 imputations, to impute data to a monotone missing data pattern under a MAR assumption.

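### The exploratory EM/CM equal-effect test in SAP 12.3.7 pools one covariance matrix over groups with planning SDs of 3.1 and 5.8, so at the planned mix its nominal 5% level may be nearer 1–3%

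*SAP*

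**What the plan says.** SAP 12.3.7 lists the subgroups for the primary endpoint, among them EM versus CM as re-derived from baseline diary data. It specifies two outputs. The first is the 12.3.2 model fitted separately on the patients of each subgroup. The second is an equal-effect test: "The assumption of equal treatment effect across subgroups will be investigated on an exploratory basis for all subgroups listed above". The test adds the subgroup-by-treatment-by-time term to the model and is described as "A test for whether the 3-way interaction term and the 2-way interaction (subgroup-by-treatment) term can be removed from the model". The method follows: "This will be done by fitting both models using (maximum likelihood) ML and making a likelihood ratio test", with the asymptotic chi-square as reference and the p-value reported.

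The model being extended is that of SAP 12.3.2, where "An unstructured variance structure will be used to model the within-patient errors". The only code given for it, in SAP Appendix IV, reads "repeated AVISITN / subject = USUBJID type = UN" and has no `group=` option. No sentence in 12.3.7 lets the covariance differ between subgroup levels in the interaction test.

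SAP section 16 and protocol 16.10 take the planning inputs from the two earlier Phase III studies. For EM the effects are 0.69 (100 mg) and 1.11 (300 mg) with SD 3.1. For CM they are 2.03 and 2.60 with SD 5.8. The assumed mix is 40% EM and 60% CM.

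**The concern.** A pooled covariance estimate gives the wrong variance for a between-group contrast when the groups differ in both spread and size. Here the variance ratio is (5.8/3.1)² = 3.5, and the less variable group, EM, is also the smaller one. The pooled matrix is dominated by CM patients, so it overstates the uncertainty of the EM effect by more than it understates that of the CM effect. The likelihood ratio statistic comes out too small and the test rejects too rarely.

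EM versus CM is the one listed subgroup for which the plan's own inputs show different effects. A large p-value from this test could be read as support for equal benefit in the two populations when it partly reflects the covariance assumption. The plan is also uneven here: the separate subgroup fits let EM and CM have their own covariance, while the p-value reported beside them does not.

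**Working it through.** **Inputs.** From SAP section 16 and protocol 16.10: 280 per arm, 2% without post-baseline data (280 × 0.98 = 274.4), EM share p = 0.4, SDs 3.1 and 5.8, and the effects above. From SAP 12.3.2: six months and three treatments. Two assumptions are not in the documents: the SD ratio applies to baseline-adjusted monthly residuals, and the within-patient correlation is the same in EM and CM.

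**The plan's own power first.**
- Mixed SD: √(0.4 × 3.1² + 0.6 × 5.8²) = √24.03 = 4.90. SE: 4.90 × √(2/274.4) = 0.4185.
- 100 mg: effect 0.4 × 0.69 + 0.6 × 2.03 = 1.494, power 94.6% (stated: about 94%).
- 300 mg: effect 0.4 × 1.11 + 0.6 × 2.60 = 2.004, power 99.8% (stated: 99%).

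Both agree with the plan, so the inputs are read as intended.

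**Degrees of freedom.** For a two-level subgroup, subgroup-by-treatment has 2 and the three-way term has 2 × 5 = 10, so 12 in all. The 5% critical value is 21.03.

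**Variance of the EM-minus-CM difference in effect, one dose against placebo.**
- True: 2 × 3.1²/109.8 + 2 × 5.8²/164.6 = 0.58, SE 0.764.
- Pooled: 24.03 × (2/109.8 + 2/164.6) = 0.73, SE 0.854.

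The ratio is λ = [(1−p) × 3.1² + p × 5.8²] / [p × 3.1² + (1−p) × 5.8²] = 19.22/24.03 = 0.80.

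**Size.** Under equal effects the pooled statistic behaves approximately as λ times a chi-square on 12 df, so size = P(χ²₁₂ > 21.03/λ).

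| SD ratio | λ | 21.03/λ | size at 40% EM |
|---|---|---|---|
| 1.87 (plan's SDs) | 0.80 | 26.28 | 0.98% |
| 1.4 | 0.878 | 23.94 | 2.1% |
| 1.2 | 0.930 | 22.60 | 3.1% |

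Simulating the ML likelihood ratio test (823 patients, complete six-month data, baseline covariate) gives 1.3%, or 1.4% with 17 assumed countries in the model. With equal SDs and the same country terms, simulated size at 40% EM is 5.9%, so the shift comes from the unequal variances. Two settings with different within-patient correlations in EM and CM gave 2.0% and 2.5%: same direction, smaller shift.

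**Power of the planned 12-df test.** Hold the plan's effects constant over months. The EM-CM differences are 2.03 − 0.69 = 1.34 and 2.60 − 1.11 = 1.49. The two dose contrasts share the placebo arm, so the combined quantity is 1.34² + 1.49² − (1.34 + 1.49)²/3 = 1.346. With a common monthly correlation ρ, the noncentrality is 1.346 × [6/(1+5ρ)] / (0.584/2).
- SDs taken as monthly SDs: 7.9 at ρ = 0.5 and 5.8 at ρ = 0.75.
- SDs taken as those of the 12-week average (multiply by (1+2ρ)/3): 5.3 and 4.9.

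Power with the correct covariance, P(χ²₁₂ > 21.03 at that noncentrality), runs from 24% to 40%. With the pooled covariance the threshold becomes 26.28, and power runs from 9% to 19%.

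**After the change.** With a separate unstructured matrix for EM and CM in both fits, simulated size at 40% EM is 5.2% (4,000 runs, no covariates).

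**The case against.** The strongest reply is that nothing depends on this p-value. The test is labelled exploratory, sits outside the testing strategy, has no decision threshold of its own, and triggers no action. The separate subgroup fits already give each population an estimate with its own covariance, so a reader can compare EM and CM directly. All of that stands, and it sets the grade. It does not make the reported p-value correct.

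A second reply is that 3.1 and 5.8 are planning SDs for the 12-week endpoint in two earlier studies, while the test depends on monthly residuals after baseline adjustment, whose SDs are not given. This also stands, which is why a range is shown and not one figure. A third is that power is poor even with the right covariance. That is true: the change corrects the level and recovers some power, but a non-significant result would still say little.

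Stronger readings are tempting and should be resisted:
- **An inflated test.** A reader might infer that the error could become anti-conservative, since the same formula gives about 16% (simulated 17%) at 60% EM. That share is purely hypothetical. The plan aims for about 40% EM, and the re-derived classification tends to lower it. Criterion D of SAP 4.5.1 has no minimum duration, whereas the randomisation algorithm in Appendix III requires 30 minutes, and prorating can only raise a count. On the definitions shown, patients would move from EM to CM.
- **The low/high-frequency EM split.** The documents give no SDs for these two groups, so miscalibration between them cannot be claimed. Only the EM-versus-CM contrast in that row is supported.
- **Single-contrast power losses.** Power for one averaged dose contrast describes a different test from the 12-df one planned.

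**Conclusion.** The point holds as a minor one. With one common covariance matrix, the EM/CM equal-effect test is conservative at the planned 40:60 mix. Its size is about 1% if the planning SD ratio of 1.87 applies to the baseline-adjusted monthly residuals, and about 2–3% if that ratio is 1.4 to 1.2. Under the plan's effects, power is roughly 9–19% where a correct covariance would give 24–40%.

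These figures rest on complete data, effects constant over months, monthly correlations of 0.5–0.75, and equal correlation in the two groups. They show the direction and approximate size of the error, not a precise level. The primary and key secondary tests and the separately fitted subgroup estimates are untouched.

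**What to change.** In SAP 12.3.7, state that for the EM/CM interaction test both nested ML models are fitted with a separate unstructured matrix for each subgroup level: `repeated AVISITN / subject=USUBJID type=UN group=<EM/CM>`. If either fit fails to converge, apply the SAP 12.3.2 fallback structures in the same order, keeping `group=` and using the same structure in both models. For the low/high-frequency EM and CM row the same option may be used with EM versus CM as the grouping.

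The cost is one sentence, one code option and 21 more covariance parameters (a 6 × 6 matrix has 6 × 7/2 = 21), estimated from about 820 patients. No data collection or confirmatory analysis changes.

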12.4 Analysis Methodology for the Key Secondary Endpoints

12.4.1 Key Secondary Estimands

The key secondary endpoints 50% response (Weeks 1-12), 75% response (Weeks 1-12), and change from baseline in MMDs (Weeks 13-24) are all derived based on the number of MMDs for the relevant intervals.

Therefore, the key secondary estimands can be formulated similarly to the primary estimand described in Section 12.3.1, with the following modifications in regards to endpoint and population-level summary attributes. The binary 50% and 75% response variables across three 4-week intervals are calculated based on the available monthly values. Further details on the derivation of the endpoints can be found in Section 19.1.1.

50% response (Weeks 1-12)

- The **endpoint** to be obtained is a binary response variable indicating a successful response if a patient has achieved a 50% reduction or more in number of MMDs across weeks 1-12
- The **population-level summary** is the odds ratio of a successful response between eptinezumab and placebo

75% response (Weeks 1-12)

- The **endpoint** to be obtained is a binary response variable indicating a successful response if a patient has achieved a 75% reduction or more in number of MMDs across weeks 1-12
- The **population-level summary** is the odds ratio of a successful response between eptinezumab and placebo

Change from baseline in MMDs (Weeks 13-24)

• The endpoint to be obtained is the change from baseline in MMDs across weeks 13-24

• The **population-level summary** is the least squares mean difference between eptinezumab and placebo for the endpoint

Change from Baseline in HIT-6

For HIT-6, some of the intercurrent events will be addressed using different strategies than what is described for the primary and other key secondary estimands. Therefore, the phrasing of the key secondary estimand related to this endpoint is also a little different.

The differences to the strategies used for the primary and other key secondary estimands in the handling of intercurrent events are as follows:

- *Use of acute medication to treat a headache:* Instead of a hypothetical strategy, this intercurrent event will be handled using a treatment policy strategy, i.e. the values of HIT-6 are used regardless of whether the patient took any acute medication because they believed they were experiencing a migraine
- *Withdrawal due to lack of efficacy*: Will be addressed using a treatment policy strategy where the available values of HIT-6 are used regardless of patients withdrawing due to lack of efficacy
- *Withdrawal due to adverse event*: Will be addressed using a treatment policy strategy where the available values of HIT-6 are used regardless of patients withdrawing due to adverse events

Based on this, the key secondary estimand for evaluating the health-related quality of life and work productivity impact objective of the study will be the effect of eptinezumab on change from baseline in HIT-6 score regardless of patients withdrawing due to lack of efficacy or adverse events and regardless of use of acute or preventive migraine medication and infusion interruptions or terminations.

In addition, the following two attributes differ from the primary and other key secondary estimands:

- The endpoint to be obtained is the change from baseline in HIT-6 at Week 12
- The **population-level summary** is the least squares mean difference between eptinezumab and placebo for the endpoint

